## 4.7 SAFETY ANALYSES

All safety analyses will be based on the safety population. For all change from baseline analyses, unless noted otherwise, baseline will be defined as the last non-missing value on or before the first infusion.

Treatment emergent AEs (TEAEs) are defined as AEs that occur on or after treatment on Day 1 or existing events that worsened after first study dose. Treatment emergent serious AEs (SAEs) are defined as SAEs that occur on or after treatment on day 1 or existing events that increased in severity after first study dose. AEs will be coded using the current MedDRA Dictionary and summarized by NCI CTCAE v4.0 grade.

Relapse is part of the efficacy outcome as a component of protocol defined events and will be reported in the efficacy results section.

Visit windows will be used in analyses that summarize laboratory measurements, vital signs. Visit window specifications will be provided in the separate Module 2.

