5.2.2 Serious Adverse Events (Immediately Reportable to the Sponsor)

A serious adverse event is any adverse event that meets any of the following criteria:

- Is fatal (i.e., the adverse event actually causes or leads to death)

Ocrelizumab—Genentech, Inc.

46/ Protocol MN30035, Version 5

- Is life threatening (i.e., the adverse event, in the view of the investigator, places the patient at immediate risk of death)
This does not include any adverse event that had it occurred in a more severe form or was allowed to continue might have caused death.
- Requires or prolongs inpatient hospitalization (see Section [5.3.5.11](#))
- Results in persistent or significant disability/incapacity (i.e., the adverse event results in substantial disruption of the patient's ability to conduct normal life functions)
- Is a congenital anomaly/birth defect in a neonate/infant born to a mother exposed to study drug
- Is a significant medical event in the investigator's judgment (e.g., may jeopardize the patient or may require medical/surgical intervention to prevent one of the outcomes listed above)

The terms "severe" and "serious" are not synonymous. Severity refers to the intensity of an adverse event (e.g., rated as mild, moderate, or severe, or according to NCI CTCAE; see Section [5.3.3](#)); the event itself may be of relatively minor medical significance (such as severe headache without any further findings).

Severity and seriousness need to be independently assessed for each adverse event recorded on the eCRF.

Serious adverse events are required to be reported by the investigator to the Sponsor immediately (i.e., no more than 24 hours after learning of the event; see Section [5.4.2](#) for reporting instructions).

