5.3.5.4 Persistent or Recurrent Adverse Events

A persistent adverse event is one that extends continuously, without resolution, between patient evaluation timepoints. Such events should only be recorded once on the Adverse Event eCRF. The initial severity (intensity or grade) of the event will be recorded at the time the event is first reported. If a persistent adverse event becomes more severe, the most extreme severity should also be recorded on the Adverse Event eCRF. If the event becomes serious, it should be reported to the Sponsor immediately (i.e., no more than 24 hours after learning that the event became serious; see Section 5.4.2 for reporting instructions). The Adverse Event eCRF should be updated by changing the event from "non-serious" to "serious," providing the date that the event became serious, and completing all data fields related to serious adverse events.

A recurrent adverse event is one that resolves between patient evaluation timepoints and subsequently recurs. Each recurrence of an adverse event should be recorded as a separate event on the Adverse Event eCRF.

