5.3.5.9 Preexisting Medical Conditions

A preexisting medical condition is one that is present at the screening visit for this study. Such conditions should be recorded on the General Medical History and Baseline Conditions eCRF.

A preexisting medical condition should be recorded as an adverse event only if the frequency, severity, or character of the condition worsens during the study. When recording such events on the Adverse Event eCRF, it is important to convey the concept that the preexisting condition has changed by including applicable descriptors (e.g., "more frequent headaches").

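### SAP 4.7 lets an existing event count as a treatment-emergent SAE because its severity rose, without requiring that it be serious

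*SAP*

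**What the plan says.** SAP 4.7 gives two parallel definitions. TEAEs are "AEs that occur on or after treatment on Day 1 or existing events that worsened after first study dose". Treatment-emergent SAEs are "SAEs that occur on or after treatment on day 1 or existing events that increased in severity after first study dose". Both sentences extend to existing events, and neither restricts that phrase to serious ones.

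Protocol 5.2.2 decides seriousness by a list of outcomes: "A serious adverse event is any adverse event that meets any of the following criteria". It then separates the two concepts. "Severity refers to the intensity of an adverse event", and "Severity and seriousness need to be independently assessed for each adverse event recorded on the eCRF".

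Three protocol rules govern which records exist:

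- Section 5.3.5.9: a pre-existing condition "should be recorded as an adverse event only if the frequency, severity, or character of the condition worsens during the study".
- Section 5.3.5.4: when a persistent event turns serious, the site updates the same record, "providing the date that the event became serious".
- Section 5.3.1: between consent and first dose, the only events reported are SAEs caused by a procedure the protocol requires.

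In SAP 2.2.5, one outcome uses the defined term: the frequency of patients with serious treatment-emergent events. SAP 4.7.2 plans serious AE summaries and a serious AE rate per 100 patient-years, but does not label these treatment-emergent. SAP 4.8 shows that seriousness is a separate data field with its own rule for missing values.

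**The concern.** The second part of the SAE definition puts severity where seriousness belongs. An event can become more intense without meeting any outcome on the Protocol 5.2.2 list, and the SAP sentence would still call it a treatment-emergent SAE.

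Safety, measured by the nature and incidence of adverse events, is the trial's secondary objective, and the count of patients with serious events is one of its main summaries. The study has a single arm, so there is no control group in which the same misclassification would appear and be visible. Protocol 6.6.2 plans a listing of all SAEs, which would let a reader spot a misclassified event. The main-study text of SAP 4.7.2 mentions listings only for withdrawals due to adverse events and for deaths.

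**Working it through.** The SAP gives no figure to reproduce. The check applies the literal SAP 4.7 wording to the possible cases and compares each result with Protocol 5.2.2. Existing events are taken to include conditions present at screening that later become AE records under Protocol 5.3.5.9.

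| Case | Serious under Protocol 5.2.2? | First part of SAP 4.7 (SAE on or after Day 1) | Second part (existing event, severity rose) | Result |
|---|---|---|---|---|
| A. Pre-existing condition, Grade 1 to Grade 2 after dosing, no seriousness criterion met | No | No | Yes | Counted, wrongly |
| B. Pre-existing condition, more frequent after dosing, same grade, not serious | No | No | No | Not counted, correctly |
| C. Onset before Day 1, meets a seriousness criterion after dosing, grade unchanged | Yes | Only if occurrence means the date it became serious | No | May be missed |
| D. Onset on or after Day 1, later turns serious | Yes | Yes | Not needed | Counted, correctly |

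**Case A** is the real conflict. Protocol 5.3.5.9 creates the AE record, the seriousness field says no, and the SAP sentence says yes.

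**Case B** limits the over-count. Protocol 5.3.5.9 covers worsening in frequency, severity or character; the SAP's second part responds only to severity. The protocol's own illustration, headaches that become more frequent, is a change in frequency and would not trigger it.

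**Case C** needs a pre-dose record of an event that was not yet serious. Protocol 5.3.1 restricts pre-dose reporting to procedure-caused SAEs, so such records should hardly exist.

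**Case D** covers an event that starts on treatment and later turns serious; the first part captures it.

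**Alternative reading.** If existing events is read as existing serious events, Case A drops out. Case C is unchanged, because the event was not serious before dosing and its grade did not rise.

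**Scale only.** With about 600 treated patients, one misclassified patient adds 1/600 = 0.17 percentage points, and six add 6/600 = 1.0 point. For reference, the 6.9% of patients with SAEs on ocrelizumab in the pooled RMS Phase III studies (Protocol 1.2.1.2) would correspond to 0.069 × 600 = 41.4 patients here. The documents do not say how many patients would fall in Case A.

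**The case against.** The best defence is that the sentence mirrors the TEAE sentence before it, so existing events is shorthand for existing events of the kind being defined, namely SAEs. Seriousness is assessed for every AE, has its own field, and is defined in the protocol; nothing in the SAP claims to replace those criteria. A programmer would very likely use the field. Data-collection rules also leave the second part little to act on: pre-dose records should already be serious, and a worsened pre-existing condition enters as a new AE record that can be tested for seriousness directly.

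Much of this stands, and it is why the practical effect is probably small. It does not make the wording right. The TEAE sentence uses the same phrase for any event, no other SAP text narrows it, and a programmer who applied the seriousness field to the second part would be departing from the written definition.

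A reader might infer four stronger points that the documents do not support:

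- **Every worsened pre-existing condition becomes an SAE.** Only a rise in severity triggers the second part.
- **Events that turn serious are generally missed.** That is confined to Case C. Protocol 5.3.5.11 also excludes from SAEs elective admissions for pre-existing conditions that have not worsened.
- **All serious-event outputs depend on this definition.** In SAP 2.2.5 only one outcome uses the term. Those on related SAEs and on SAEs that led to stopping treatment do not, and SAP 4.7.2 does not say which derivation it uses.
- **The inflation can be stated as a percentage.** That needs the share of patients with a non-serious rise in grade of a pre-existing condition, which neither document gives.

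**Conclusion.** The definition is wrong as written: it admits events that are not serious under Protocol 5.2.2, and the SAP does not correct this elsewhere. The firm consequence is a possible over-count of patients with serious treatment-emergent events (SAP 2.2.5). An effect on the SAP 4.7.2 serious AE summaries and rates is conditional on the same derivation being used there. The over-count assumes that the second part is programmed literally and that some patients have a pre-existing condition that rises in grade without becoming serious.

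The effect is probably small and cannot be quantified from the documents. The missed-event route exists but should be rare. This is a defect of wording and derivation in a descriptive safety summary, worth correcting because the remedy is simple.

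**What to change.** Replace the SAP 4.7 sentence with: *Treatment-emergent SAEs are TEAEs that meet a Protocol 5.2.2 seriousness criterion, including existing events whose date of becoming serious is on or after the first dose.* Keep the worsening test only in the TEAE definition.

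This removes Case A, because seriousness is now required, and settles Case C, because the date of becoming serious decides it.

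The cost is one sentence in the SAP and a matching derivation. The seriousness field and the date an event became serious are already collected on the AE eCRF, so no new data are needed.

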#### **4.7.1        Exposure of Study Medication**

Patients will be considered to have received a dose of treatment if they were administered at least part of one infusion of a dose (including day 1 or day 15 for the first dose).

The treatment duration (weeks) and the number of doses received (day 1 and day 15 infusions are considered as one dose) will be summarized.

The number and percent of patients with study treatment intervention and the type of intervention (slowed down, interrupted, or discontinued infusion) will be summarized. The summaries will be presented by dose (dose 1 day 1, dose 1 day 15, dose 2, dose 3, dose 4) and overall.

Kaplan-Meier plots of time to discontinuation of study treatment will be presented.

#### **4.7.2        Adverse Events**

All TEAE will be coded, summarized by NCI CTCAE v4.0 grade, and tabulated by body system and Preferred Term for individual adverse events within each body system.

Grade 3 to 5 adverse events, serious adverse events, adverse events leading to treatment discontinuation, time to withdrawal from treatment due to an adverse event, adverse events leading to infusion adjustment, and treatment-related adverse events will be summarized. In addition, all adverse events leading to withdrawal from treatment and deaths will be listed if applicable.

Number of events per 100 Patient-Years along with 95% exact confidence intervals will be summarized for all AE, serious AE and serious infections.

The number and percentage of patients with at least one infusion related reaction (IRR), and the intensity (highest grade for each patient) will be summarized in total, by dose (dose 1 day 1, dose 1 day 15, dose 2, dose 3, dose 4) and by pre-medication. In

addition, the total number of IRRs will be summarized (multiple events will be counted) in total and by dose.

#### **4.7.3 Laboratory Data**

Associated laboratory parameters, such as hepatic function, renal function, and hematology values, will be grouped and presented together. A summary of the number and percentage of patients with abnormal laboratory outcomes will be produced for each parameter.

#### **4.7.4 Vital Signs**

Changes in physical findings and vital signs with onset on or after the first OCR infusion will be summarized at each scheduled visit.

#### **4.7.5 Safety Endpoints of Special Interest**

All reported AESI will be summarized overall and by NCI CTCAE v4.0 grade, and tabulated by specific MedDRA bucket terms and preferred terms. The following types of events are of special interest:

- Drug-induced liver injury
- Suspected transmission of an infectious agent via product

### **4.8 MISSING DATA**

AEs with missing relationship to study drug will be considered as 'Related'. AEs with missing CTCAE grade will be imputed as grade 3. AE with missing seriousness will be graded as serious.

Missing and partial dates for AEs and concomitant medications will be handled according to Roche STREAM algorithm.

### **4.9 INTERIM ANALYSES**

Two interim analyses were performed during the course of the study, according to patient enrollment and availability of data of interest. Interim analyses were used for hypothesis generation, abstraction/publication for major scientific conferences, or other purposes, as applicable. The statistical analysis plan of the interim analyses were detailed and documented in a separate *DAP Module 1 CHORDS Study\_Interim\_v1.0*.

Since no adjustment of the study design or course are planned as a result of the interim looks, no adjustments to the type I error will be applied.

## **Appendix 1** **Protocol Synopsis**

|                         |  |
|-------------------------|--|
| TITLE:           | AN OPEN-LABEL STUDY TO EVALUATE THE EFFECTIVENESS AND SAFETY OF OCRELIZUMAB IN PATIENTS WITH RELAPSING REMITTING MULTIPLE SCLEROSIS WHO HAVE HAD A SUBOPTIMAL RESPONSE TO AN ADEQUATE COURSE OF DISEASE-MODIFYING TREATMENT |
| PROTOCOL NUMBER: | MN30035  |
| VERSION NUMBER:  | 5  |
| EUDRACT NUMBER:  | Not applicable   |
| IND NUMBER:      | 100,593  |
| TEST PRODUCT:    | Ocrelizumab (RO4964913)  |
| PHASE:           | IIIb   |
| INDICATION:      | Relapsing remitting multiple sclerosis   |
| SPONSOR:         | Genentech, Inc.  |

### **Objectives and Endpoints**

#### **Primary Objective**

The primary objective of this study is to assess the effectiveness of ocrelizumab 600 mg intravenously (IV) every 24 weeks over 96 weeks in patients with relapsing remitting multiple sclerosis (RRMS) who have had a suboptimal response to an adequate course of a disease-modifying treatment (DMT).

A suboptimal response is defined by having one or more clinically reported relapse(s), OR one or more T1 gadolinium (Gd)-enhanced lesion(s), OR two or more new or enlarging T2 lesions on magnetic resonance image (MRI) despite being on a stable dose of the same DMT for at least 6 months. In addition, in patients receiving stable doses of the same approved DMT for more than a year, the event must have occurred within the last 12 months of treatment with this DMT.

#### **Secondary Objective**

The secondary objective of this study is to evaluate the safety and tolerability of ocrelizumab 600 mg IV given every 24 weeks in patients with RRMS who have had a suboptimal response to an adequate course of a DMT as measured by the nature and incidence of adverse events.

#### **Exploratory Objective**

The exploratory objective of this study is to further assess the effectiveness of ocrelizumab by monitoring patient-reported outcomes (PROs) related to quality of life and treatment satisfaction.

### **Study Design**

#### **Description of the Study**

This study is a prospective, multicenter, open-label, effectiveness, and safety study in patients with RRMS who have had a suboptimal response to an adequate course of a DMT. This study will be conducted in North America. An adequate course of prior DMT is defined as the same DMT administered for at least 6 months. Ocrelizumab will be administered as an initial dose of two 300-mg infusions (600 mg total) separated by 14 days (i.e., Days 1 and 15) followed by one 600-mg infusion every 24 weeks for the study duration.

**Ocrelizumab—Genentech, Inc.**

31/Statistical Analysis Plan MN30035

Patients will be assessed for effectiveness and safety every 24 weeks. The study will consist of the following periods, described in detail below:

- Screening Period: Up to 4 weeks
- Treatment Period: Open-label treatment period of 72 weeks (4 doses)
- Safety Follow-up Period: Observation 24 weeks after the last infusion of study drug for patients who discontinue or who chose not to continue with commercially available ocrelizumab at the end of study

*Eligible patients may choose to participate in an optional shorter infusion substudy at the Week 96 visit, during which they will receive ocrelizumab infused over a shorter time period than the approved administration rate (Appendix 2).*

### **Number of Patients**

This study will enroll approximately 600 patients with RRMS who have had a suboptimal response to an adequate course of a DMT.

### **Target Population**

#### Inclusion Criteria

Patients must meet the following criteria for study entry:

- Signed Informed Consent Form
- Able to comply with the study protocol, in the investigator's judgment
- Age 18–55 years, inclusive
- Have a definite diagnosis of multiple sclerosis (MS), confirmed per the revised 2010 McDonald criteria (Polman et al. 2011; Appendix 4), and have the relapsing remitting form of MS
- Have a length of disease duration, from first symptom, of  $\leq$  12 years
- Have been treated with an adequate course of treatment with no more than three prior DMTs
  - Adequate treatment is defined as  $\geq$  6 months on a DMT.
  - Discontinuation of the most recent adequately used DMT must have been due to suboptimal response as defined below.
- Suboptimal response while on his/her last adequately used DMT (for  $\geq$  6 months); a suboptimal response is defined by having one of the following qualifying events despite being on a stable dose of the same DMT for at least 6 months:
  - One or more clinically reported relapse(s)
  - OR one or more T1 Gd-enhanced lesion(s)
  - OR two or more new or enlarging T2 lesions on MRI

These qualifying events must have occurred while on the last adequately used DMT. In addition, in patients receiving stable doses of the same approved DMT for more than a year, the event must have occurred within the last 12 months of treatment with this DMT from the date of screening.

- Expanded Disability Status Scale (EDSS) of 0 to 5.5, inclusive, at screening
- For women of childbearing potential: *agreement to use an acceptable birth control method:*
  - *Progesterone-only oral hormonal contraception, where inhibition of ovulation is not the primary mode of action*
  - *Male or female condom with or without spermicide*
  - *Cap, diaphragm, or sponge with spermicide*
  - *A combination of male condom with either cap, diaphragm, or sponge with spermicide (double-barrier methods are also considered acceptable, but not highly effective, birth control methods)*

### Exclusion Criteria

Patients who meet any of the following criteria will be excluded from study entry:

- History of primary progressive multiple sclerosis (PPMS), progressive relapsing multiple sclerosis (PRMS), or secondary progressive multiple sclerosis (SPMS)
- Inability to complete an MRI (contraindications for MRI include but are not restricted to claustrophobia, weight, pacemaker, cochlear implants, presence of foreign substances in the eye, intracranial vascular clips, surgery within 6 weeks of entry into the study, coronary stent implanted within 8 weeks prior to the time of the intended MRI, inability to tolerate Gd-enhancing ligands, etc.).
- Known presence of other neurological disorders, including but not limited to, the following:
  - History of ischemic cerebrovascular disorders (e.g., stroke, transient ischemic attack) or ischemia of the spinal cord
  - History or known presence of central nervous system (CNS) or spinal cord tumor (e.g., meningioma, glioma)
  - History or known presence of potential metabolic causes of myelopathy (e.g., untreated vitamin B12 deficiency)
  - History or known presence of infectious causes of myelopathy (e.g., syphilis, Lyme disease, human T-lymphotropic virus 1 [HTLV-1], herpes zoster myelopathy)
  - History of genetically inherited progressive CNS degenerative disorder (e.g., hereditary paraparesis; MELAS [mitochondrial myopathy, encephalopathy, lactic acidosis, stroke] syndrome)
  - Neuromyelitis optica
  - History or known presence of systemic autoimmune disorders potentially causing progressive neurologic disease (e.g., lupus, anti-phospholipid antibody syndrome, Sjogren's syndrome, Behcet's disease)
  - History or known presence of sarcoidosis
  - History of severe, clinically significant brain or spinal cord trauma (e.g., cerebral contusion, spinal cord compression)
  - History of progressive multifocal leukoencephalopathy (PML)
- Pregnancy or lactation, or intention to become pregnant during the study
  - Women of childbearing potential must have a negative serum or urine pregnancy test result within 14 days prior to initiation of study drug.
- Any concomitant disease that may require chronic treatment with systemic corticosteroids or immunosuppressants during the course of the study
- Lack of peripheral venous access
- Significant, uncontrolled disease, such as cardiovascular (including cardiac arrhythmia), pulmonary (including obstructive pulmonary disease), renal, hepatic, endocrine, and gastrointestinal or any other significant disease that may preclude patient from participating in the study
- Congestive heart failure (New York Heart Association [NYHA] Class III/IV functional severity)
- Known active bacterial, viral, fungal, mycobacterial infection or other infection (including tuberculosis [TB] or atypical mycobacterial disease but excluding fungal infection of nail beds) or any severe episode of infection requiring hospitalization or treatment with IV antibiotics within 4 weeks prior to baseline visit or oral antibiotics within 2 weeks prior to baseline visit
- History of or currently active primary or secondary immunodeficiency
- History or known presence of recurrent or chronic infection (e.g., HIV, syphilis, TB)
- History of recurrent aspiration pneumonia requiring antibiotic therapy

- History of malignancy, including solid tumors and hematological malignancies, except basal cell, *in situ* squamous cell carcinoma of the skin, and *in situ* carcinoma of the cervix of the uterus that have been excised with clear margins
- History of severe allergic or anaphylactic reactions to humanized or murine monoclonal antibodies
- History of coagulation disorders
- History of alcohol or drug abuse within 24 weeks prior to screening
- Previous treatment with natalizumab within 12 months prior to screening unless failure was due to confirmed, persistent anti-drug antibodies
  - Patients previously treated with natalizumab will be eligible for this study only if duration of treatment with natalizumab was < 1 year and natalizumab was not used in the 12 months prior to screening. Anti-JCV antibody status (positive or negative) and titer (both assessed within the year of screening) must be documented prior to enrollment. When assessed, anti-JCV antibody status should be determined using an analytically and clinically validated immunoassay (e.g., ELISA).
- Previous treatment with systemic cyclophosphamide, azathioprine, mycophenolate mofetil, cyclosporine, or methotrexate
- Treatment with IV immunoglobulin within 12 weeks prior to baseline
- Treatment with dalfampridine (Ampyra®) unless on stable dose for  $\geq$  30 days prior to screening
  - Wherever possible, patients should remain on stable doses throughout the treatment period.
- Receipt of a live vaccine within 6 weeks prior to baseline; in rare cases when patient requires vaccination with a live vaccine, the screening period may need to be extended but cannot exceed 8 weeks
- Systemic corticosteroid therapy within 4 weeks prior to screening
  - The screening period may be extended (but cannot exceed 8 weeks) for patients who have used systemic corticosteroids for their MS before screening.
  - There should be 4 weeks from last dose of systemic corticosteroid therapy prior to first infusion.
- Previous treatment with fingolimod (Gilenya®) or dimethyl fumarate (Tecfidera®) in patients whose lymphocyte count is below the lower limit of normal (LLN)
- Contraindications to or intolerance of oral or IV corticosteroids, including IV methylprednisolone (or equivalent steroid) administered according to the country label, including:
  - Psychosis not yet controlled by a treatment
  - Hypersensitivity to any of the constituents preceding
- Treatment with alemtuzumab (Lemtrada®)
- Treatment with a B-cell targeted therapies (e.g., rituximab, ocrelizumab, atacicept, belimumab, or ofatumumab)
- Treatment with a drug that is experimental (Exception: treatment with an experimental drug that was subsequently approved in the patient's country is allowed.)
- Laboratory test results as follows:
  - Positive screening tests for hepatitis B (hepatitis B surface antigen [HBsAg] positive, or positive hepatitis B core antibody [total HBcAb] confirmed by a positive viral DNA polymerase chain reaction [PCR]) or hepatitis C antibody (HepCAb)
  - Lymphocyte count below LLN
  - CD4 count  $< 300/\mu\text{L}$
  - AST or ALT  $\geq 3.0 \times$  the upper limit of normal (ULN)

- Platelet count < 100,000/ $\mu$ L (<  $100 \times 10^9/L$ )
- Total neutrophil count below LLN
 

Re-testing before baseline: in rare cases in which the screening laboratory samples are rejected by the laboratory (e.g., hemolyzed sample) or the results are not assessable (e.g., indeterminate) or abnormal, the tests need to be repeated. Any abnormal screening laboratory value that is clinically relevant should be retested in order to rule out any progressive or uncontrolled underlying condition. The last value before enrollment must meet study criteria. In such circumstances, the screening period may need to be prolonged but should not exceed 8 weeks.

